Data were collected on-line via a free and open iOS application, “DiagnosUs”, created by Centaur Labs as a platform for game-like image labeling competitions <https://www.centaurlabs.com/>). Between 6/22/21 and 6/27/21, Centaur Labs ran 24 ‘contests’ on our behalf, collecting >300,000 trials from 803 participants in 6 days. Each of the 24 contests consisted of 80 unique images of a skin lesion as shown in Figure 1. This is a relatively small number of images, but it kept the sessions short and encouraged participation. Images came from the International Skin Imaging Collaboration (ISIC) 2018 challenge (Codella, et al., 2019). The set contains over 1,200 melanoma images and over 7,600 nevus images.

[figure not shown]

Figure 1: Sample stimulus displays. Left: Participants are asked if a lesion is a melanoma (cancer) or a nevus (benign ‘mole’). Right: After response, if this were a feedback condition, red or green feedback would inform the observer of the correctness of the answer. In no feedback conditions, neutral feedback indicated that the response had been registered.

On each of the six days, there were four contests available. These were:

- 1) Low Prevalence – No Feedback; consisting of 20% (16) melanoma images
- 2) Low Prevalence – Feedback; prevalence was the same as in #1, but with accurate, trial by trial feedback
- 3) High Prevalence – No Feedback; consisting of 50% (40) melanoma images
- 4) High Prevalence – Feedback; prevalence was the same as in #3, but with accurate, trial by trial feedback

The contests were randomly assigned to participants with the constraint that they did not run the same type of contest more than once in a day. Participants could take part in as many or as few contests as they wished over the course of the six days and they could end up repeating a

condition from one day on another day. The prevalence and feedback conditions were not advertised to participants. Accuracy is the main dependent variable though we also collected response times.

Because of the on-line, voluntary nature of the data collection, we did not have control over the viewing conditions or the type of screen used. We compensated by collecting a very large dataset (see below).

Observers

We collected data from 803 unique individuals. For each individual, we have a crude categorization of expertise as shown in Table 1:

Medical Student	337
Pre-Med Student	174
No Medical Experience	145
Medical Doctor	54
Other Healthcare Professional	47
Nurse	25

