Medical Technician	11
Physician Assistant	10

Table 1: Observers divided by expertise category

Participants were asked why they chose to participate and given three choices, as shown in Table 2.

Compete With Others	37
Earn Money	248
Improve My Skills	518

Table 2: Observers divided by reason to participate

Participants reported coming from 78(!) countries with three quarters of the participants coming from nine countries, as shown in Table 3.

Philippines	198
USA	182
Ghana	94
Great Britain	31
Romania	30
Canada	27
Mexico	19
Indonesia	15
Australia	13
All other	194

Table 3: Reported country of origin.

Beyond this demographic information, we have only an observer number. We were given no identifying information about the participants. Participation on the app constituted consent. Procedures were approved by the Institutional Review Board at Brigham and Women's Hospital (IRB #2007P000646).

These 803 participants produced 311,842 trials of data. An excel spreadsheet with all data is posted on the Open Science Framework at <https://osf.io/hck5n/>. From this set, we eliminated participants who did not complete a full block of 80 trials. This left 630 participants who ran a total of 277,371 trials in 2,988 blocks. Different participants chose to participate in different numbers of blocks. As shown in Table 4.

Blocks Run	# of Participants		Blocks Run	# of Participants
1	315		13	10
2	178		14	2
3	104		15	4
4	56		16	6
5	52		17	5
6	22		18	3
7	27		19	10
8	20		20	3
9	14		21	4
10	10		22	2
11	10		23	6
12	5		24	4

Table 4: Numbers of participants who ran N (1-24) blocks over 6 days of testing.

Those participants running only a single block were removed from most analyses because our primary interest is the influence of one block upon the next. Obviously, with some participants contributing 24 blocks and others contributing 2, the dataset is unbalanced. We repeated the main analyses reported below, limiting the analysis to only the first pair of blocks for each observer. This reduces power. However, the main patterns of results, reported below, are found when the dataset is restricted to only blocks 1 and 2. Accordingly, we think that the unequal numbers of trials and blocks from different participants is not a significant issue for the present study. In the results reported, we analyze results from the 2,998 remaining blocks of data.

Statistical Analysis / Results

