A one-way ANOVA shows a main effect of condition on d' ($F(3, 2076) = 6.461, p = 0.0002$, partial eta-sq = 0.01) and Šídák's multiple comparisons test shows that performance on skin cancer detection task is modestly better in the high prevalence, feedback condition than in the high prevalence, no-feedback condition ($p = 0.008$). Prevalence effects are better understood as criterion shifts. An ANOVA shows a very large main effect of condition on criterion ($F(3, 2076) = 30.16, p < 0.0001$, partial eta-sq = 0.04). Pairwise comparisons show a strong LPE effect when feedback is given ($p < 0.0001$). Criterion becomes more conservative at low prevalence. Without

feedback, criterion becomes slightly more liberal on average (0.34 to 0.31). This is not statistically significant ($p = 0.47$). As noted earlier, the PICC effect (Levari, et al., 2018), while certainly real, is typically more fragile than the LPE effect in the opposite direction (Lyu, et al., 2021). The differences between conditions with feedback and without feedback are highly significant ($p < 0.0001$ for each comparison). A significant LPE effect is seen if analysis is restricted to each participant's first block of data ($p < 0.0001$). There is no PICC effect. If all blocks of data are used, eliminating the $d' > 0.5$ filter, there is, again a significant LPE ($p < 0.0001$) and an insignificant PICC effect ($p = 0.1244$).

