Even though participants were not focused on the speed of their responses, response time data reflect the effects of prevalence and feedback. Figure 3A shows the distribution of the ~300,000 trials, divided by block type. As is typical with RT distributions, these distributions have very long positive tails. Some very long RTs probably reflect extended thought, while others might reflect checking an incoming text message. We chose to eliminate the longest 1% of RTs as outliers (>7 sec). Figure 3B shows the mean and 95% confidence intervals on a much finer scale so that the differences between conditions are more clearly visible. There is a significant effect of block type ($F(3, 299422) = 52.88$, $p < 0.0001$, partial eta-sq = 0. 0.0005). Šídák's multiple comparisons test shows that the 46 msec difference between high and low prevalence with feedback is significant ($p < 0.0001$). Low prevalence RTs are shorter than high prevalence. Without feedback, the PICC effect on RT goes in the opposite direction. Low prevalence RTs are 18 msec longer than high prevalence ($p = 0.0008$). These effects are in line with the RT effects seen in other prevalence studies ([name] & VanWert, 2010).

[figure not shown]

Figure 3: Response time as a function of block type. RTs < 7 sec were analyzed. (A) RT distributions with the graph truncated at 3 sec. Black lines show the mean. (B) Mean RT on a much finer scale. Error bars show +95% confidence intervals.

How does one block influence the next?

The block data essentially replicate previous results, collected under very different conditions. However, the key question for this study is whether or not exposure to one combination of prevalence and feedback influences the next block of trials. Blocks could be independent of each other. The effect of one block might have a transient impact on the next block (e.g. lasting for a few trials and then fading). Finally, the effect of one block on the next could be dependent on the delay between blocks (especially since that delay could be from one day to the next.). To assess

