Looking separately at changes in P(True Positive) and P(False Positive) responses, we see essentially the same pattern of results. For changes in True Positive proportions, pairs where Block 1 is low prevalence with feedback are significant (all $p < 0.005$) except when Block 2 is High Feedback ($p = 0.38$). Pairs where Block 1 is high prevalence with feedback are significant (all $p < 0.005$ except when Block 2 is Low Feedback which $p = 0.02$). The Low Feedback – High Feedback pair is not significant. For changes in False Positive proportions, pairs where Block 1 is low prevalence with feedback are significant (all $p < 0.05$). When Block 1 is high prevalence with feedback, results are significant when Block 2 is Low No Feedback, High No Feedback, and Low Feedback ($p < 0.01$). When Block 2 is High Feedback, there is no significant change ($p = 0.29$). The Low No Feedback – High Feedback pair is significant ($p = 0.001$). No other changes in P(True Positive) and P(False Positive) responses are significant. As noted above, removing the $d' > 0.5$ filter does not change the pattern of results. Limiting analysis to only the first pair of blocks for each participant preserves the direction of effects but some effects become statistically unreliable because of the loss of power.

Do the effects of one block on the next change with time between blocks?

Figure 5 shows that a block with feedback has an influence on the criterion in the next block. Is that effect transitory or persistent? The time between blocks is quite variable because participants could perform the second block immediately or from one to several days later. Accordingly, for each of the 16 pairs of blocks, we examined change in criterion as a function of time between blocks. The results are shown for four different time ranges in Figure 6.

[figure not shown]

Figure 6: Change in criterion as a function of time between the start of block 1 and start of block 2. 1440 minutes = 1 day. Colored lines are best-fit linear regressions for each of 16 pairs of block types. A) All data, B) Delay < 1 day, C) Delay < 2 hours, D) Delay < 15 min. Repeat pairs (e.g. Low Feedback -> Low Feedback) do not occur for shorter delays (C & D).

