first half and second half of the trials in block 2, separately. The results are essentially unchanged from those shown in Figure 5. Exposure to Low Prevalence with Feedback in block 1, produces a conservative shift in block 2 criterion in both the first half and the second half of block 2. All t-tests for pairs where Block 1 is Low Feedback are significant except for the Low Feedback → High Feedback pair in the first half, when the effect should be stronger than in the second half. Exposure to High Prevalence with Feedback in block 1, produces a liberal shift in block 2 criterion in both the first half and the second half of block 2. T-tests when block 2 is Low Feedback, Low No Feedback and High No Feedback are significant. T-test when block 2 is High Feedback is not significant in either half (again, recall that the High Feedback -> High Feedback pair has the fewest instances in the dataset).

The lack of any systematic decrease in the magnitude of the effects is shown in Figure 8. The mean change in criterion is plotted for the first and second half of each pair of blocks. Note the grouping of the pairs. The dark blue pairs show the conservative (positive) shift following low prevalence with feedback. The red pairs show the liberal (negative) shift following high prevalence with feedback. If the effects only lasted for the first 2-3 dozen trials, these effects should collapse toward zero in the second half. Clearly, this is not the case.

[figure not shown]

Figure 8: Mean change in criterion for the first and second halves of a block of trials.

Effects of Expertise

As noted in the Methods section, participants gave a rough categorization of their level of expertise. Sadly, this convenience population does not include any substantial number of self-identified expert dermatologists. Only one MD self-identifies as a dermatologist. We can create an expertise continuum from participants reporting no medical training to premedical students to medical students and, finally, to medical doctors. Table 6 shows the numbers of participants and the number of pairs of data contributed by each group.

Expertise category	No. of Participants	No. of pairs
Medical Doctor	54	131
Medical Student	337	952
Pre-Med Student	174	426
No Medical Experience	145	358

Table 6: Number of participants in each expertise group and the number of condition pairs contributed by the groups.

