Figure 9 shows d' and criterion as a function of expertise group, regardless of the type of feedback or prevalence (Recall, from Figure 2, that there is little effect of block type on d' .)

[figure not shown]

Figure 9: Effects of expertise category on d' and crit, regardless of prevalence and/or feedback.

There is a highly significant effect of expertise category ($F(3, 1863) = 38.58, p < 0.0001$, partial eta-squared = 0.86) and, as can be seen by the pairwise comparisons, that effect is entirely due to superior performance of the medical students (all comparisons to medical students, $p \leq 0.0001$).

It might seem disappointing that MDs were no better at this task than non-medical participants.

However, these non-dermatologist MDs may not have spent time looking at skin lesions for many years and the novices were only being asked to perform a difficult, but straight-forward, two-alternative, forced-choice discrimination. It is the medical students, many of whom may have recently been learning about skin lesions, who do somewhat better on this task. Of course, there could be other reasons for the group differences (e.g. motivated, competitive students versus more casually interested MDs. We cannot know in this case.)

There is a very modest effect of expertise category on criterion ($F(3, 1863) = 3.32, p = 0.02$, partial eta-squared = 0.01). Pairwise comparisons reveal that premedical students are slightly more conservative than medical students ($p = 0.049$). This does not appear to be a particularly meaningful finding.

In terms of the impact of expertise on the effect of block 1 on block 2, the data are noisy, with fewer pairs showing significant effects of block 1 on block 2. This seems to be a statistical power issue. The pairs that are significant are the same as those seen in Figure 4, with low prevalence on block 1 making participants more conservative on block 2 and high prevalence making them more liberal. There is no evidence for any systematic effect of expertise. In particular, there is no evidence that the most expert group (medical students) shows a different pattern of results. In

that group (fortunately, the largest), Pairs with Low Feedback as block 1 are more conservative and with High Feedback as block 1 are more liberal (all $p \leq 0.01$).

Literature Cited

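### The expertise effect size on d' reads 0.86 but its own F gives 0.06, and expertise and response time are tested on block pairs and single trials as if independent

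*Combined protocol and SAP*

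**What the plan says.** The Observers section of the Specific Protocol reports that some participants ran 24 blocks and others two. It says the main analyses were repeated on each person's first pair of blocks, and concludes: "Accordingly, we think that the unequal numbers of trials and blocks from different participants is not a significant issue for the present study".

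The one-block-per-person and one-pair-per-person checks that are actually reported cover two results. On the low prevalence effect (LPE), Statistical Analysis / Results says "A significant LPE effect is seen if analysis is restricted to each" participant's first block (p < 0.0001). On the carry-over from one block to the next, the text says "Limiting analysis to only the first pair of blocks for each participant preserves the direction of effects", while conceding that some effects lose significance.

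The RT analysis in the same section gives F(3, 299422) = 52.88. Without feedback it reports that "Low prevalence RTs are 18 msec longer than high prevalence" RTs (p = 0.0008).

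Under Effects of Expertise, "Table 6 shows the numbers of participants and the number of pairs of data contributed by each group". The effect of expertise on d' is F(3, 1863) = 38.58 with "partial eta-squared = 0.86". The effect on criterion is F(3, 1863) = 3.32, p = 0.02.

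Section VI, Biostatistical Analysis, names ANOVA as the usual method. No participant term, repeated-measures error or cluster adjustment is described anywhere.

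**The concern.** An effect size of 0.86 says that a crude self-reported training category explains most of the variation in d'. That does not fit its own F, or the text's modest description of the medical students' advantage.

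The second problem is the unit of analysis. Expertise is a fixed trait of a person, so several pairs from one physician are not several independent physicians. The 131 pairs in the Medical Doctor row come from at most 54 people. For RT, prevalence and feedback are set once per 80-trial block, but the test counts each trial. With any positive correlation within participants (expertise) or within blocks (RT), the p-values are too small and the confidence intervals too narrow.

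The RT result carries some weight. The introduction to the Specific Protocol announces weak prevalence-induced concept change (PICC) effects. The criterion tests do not show one: p = 0.47 in the filtered data, no effect in first blocks, p = 0.1244 unfiltered. The trial-level RT contrast is the only significant no-feedback prevalence contrast reported in support of PICC.

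**Working it through.** **1. Effect size.** Partial eta-squared = 3F / (3F + error df), applied to all five printed results:

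| Analysis | F | Error df | Computed | Printed |
|---|---|---|---|---|
| Condition, d' | 6.461 | 2,076 | 0.009 | 0.01 |
| Condition, criterion | 30.16 | 2,076 | 0.042 | 0.04 |
| Block type, RT | 52.88 | 299,422 | 0.0005 | 0.0005 |
| Expertise, criterion | 3.32 | 1,863 | 0.005 | 0.01 |
| Expertise, d' | 38.58 | 1,863 | **0.058** | **0.86** |

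Four of the five reproduce after rounding. A value of 0.86 would need F = (0.86/0.14) × 1,863/3, about 3,815.

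**2. Unit of analysis.** Table 6 pairs: 131 + 952 + 426 + 358 = 1,867, and 1,867 − 4 groups = 1,863. So the expertise tests count pairs. For RT, 299,422 + 4 = 299,426, which can only be single trials.

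**3. Table 6 participants.** 54 + 337 + 174 + 145 = 710. These repeat the Table 1 counts, taken before exclusions. They exceed the 630 participants retained, and also exceed the number who ran two or more blocks: 630 − 315 = 315 from the text, or 557 from Table 4. The number of people behind the 1,867 pairs is therefore not given.

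**4. Expertise under clustering.** Design effect = 1 + (m − 1) × ICC, where m is the size-weighted number of pairs per participant. With N − 1 pairs for a person with N blocks, Table 4 gives 2,537 pairs and m = 25,627/2,537 = 10.1. Random thinning to 1,867 pairs gives m = 1 + 9.1 × (1,867/2,537) = 7.7. Table 4 conflicts with the text (it sums to 872 participants, against 630), so m is approximate. F is divided by the design effect.

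| Assumed ICC | Design effect | True size of nominal 5% test | Criterion p | F for d' |
|---|---|---|---|---|
| 0.02 | 1.1–1.2 | about 8% | 0.03–0.04 | 33–34 |
| 0.1 | 1.7–1.9 | 20–25% | 0.11–0.16 | 20–23 |
| 0.3 | 3.0–3.7 | 46–55% | 0.35–0.45 | 10–13 |

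The criterion result reaches p = 0.05 at ICC 0.030 (m = 10.1) or 0.041 (m = 7.7). At ICC 0.5, F for d' is still about 7 to 9. A null simulation using Table 4 block counts and 2,080 pairs gave test sizes of 7–8%, 18–22% and 49–51% at the three ICCs, close to the formula.

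**5. RT under block-level correlation.** Design effect = 1 + 79 × ICC for 80-trial blocks. The number of comparisons in the Šídák family is not stated, so 2 to 6 were tried. Undoing the adjustment on p = 0.0008 gives z = 3.54 (2 comparisons) to 3.82 (6). Dividing z by the square root of the design effect and re-adjusting:
- the 18 ms contrast passes 0.05 at ICC 0.019 (2 comparisons) to 0.014 (6), or at 0.024 if the printed p is unadjusted;
- at ICC 0.05 its adjusted p is 0.21 to 0.42;
- for the 46 ms feedback contrast, scaling z by 46/18 (assuming similar standard errors) gives p < 0.007 at ICC 0.1.

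**6. Main criterion t-tests.** The contests were assigned so that "they did not run the same type of contest more than once in a day". Over six days a person can add at most 6 pairs to any one of the 16 cells, so the design effect is at most 1 + 5 × ICC. Simulated size-weighted multiplicity within a cell was 1.4 to 2.4, giving design effects of 1.04–1.14 at ICC 0.1 and 1.12–1.42 at ICC 0.3. The design effect that a printed p tolerates is (z/1.96)²: 1.97 for p = 0.006, 3.15 for p = 0.0005 and 1.48 for p = 0.017 (the 27-pair cell). All survive at ICC 0.3. Even at the 6-pair cap, the p < 0.006 cells hold to (1.97 − 1)/5 = 0.19. The condition ANOVA had simulated null size of about 1–5% at ICC 0.1–0.5, so it is nominal or conservative.

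**The case against.** The strongest defence is that little of substance changes. The text itself calls the criterion difference by expertise very modest and not especially meaningful. RT is secondary to accuracy by the Methods section's own statement, and its tiny effect size is printed. The study's central question is block-to-block carry-over, and there the first-pair check was done and the results hold. These points stand, and they keep this below a critical finding. They do not make the printed p-values right or extend the first-pair check to analyses for which it is not reported.

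The RT thresholds above assume correlation specific to the block. People who ran several blocks crossed conditions, so purely participant-level correlation partly cancels. Under that assumption the design effect for the 18 ms contrast is about 1.9 at ICC 0.05, not 4.95, and significance is lost at a participant ICC of about 0.06 to 0.08. That is a fair limit on the size, but the test is still inflated.

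The cluster sizes rest on Table 4, which sums to more participants (872) than were enrolled (803). The expertise figures are therefore illustrations, not estimates. With the plain average of 1,867/710 = 2.63 pairs per person, the criterion p is 0.036 at ICC 0.1 and 0.083 at ICC 0.3. That average understates the problem, because 710 is too large and unequal contributions are ignored.

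Finally, 0.86 against 0.06 is one digit and could be a text-reading error. The printed page should be checked. If it shows 0.06, that item falls away and the rest remains.

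**Conclusion.** The concern holds and should be fixed. The effect-size error needs no assumption: the stated F and df give 0.058, and the Table 6 pair total confirms the df. The unit-of-analysis problem is also certain in kind, because the error df identify pairs and trials as the units and no participant term is described.

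Its size depends on assumed ICCs. Under modest values, two secondary claims may not hold: the expertise difference in criterion and the 18 ms no-feedback RT difference. The expertise difference in d', the 46 ms RT difference with feedback (at block-level ICC up to 0.1) and the main criterion finding are not overturned. The general reassurance about unequal contributions is supported for the direction of the main criterion effects, and not for expertise or RT.

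**What to change.** - Replace 0.86 by 0.06 now, and by the model-based value after re-analysis.
- For the d', criterion and pair analyses, use mixed models with a participant random intercept, or participant-clustered or bootstrap standard errors.
- Test expertise at participant level. In Table 6, give the number of participants who actually supplied the pairs.
- Analyse RT on block means with the same participant term.
- Add a contest term only as a sensitivity analysis, if image sets differ between contests.
- Delete the general statement in the Observers section, or limit it to the direction of the main criterion effects.

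The cost is a modest re-analysis of the dataset already posted, with no new data. Some secondary p-values, notably expertise on criterion and the 18 ms RT difference, are likely to become less favourable.

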To analyze the effect of one block on the next block, we derived all the pairs of blocks in the dataset. For each of the blocks, we calculated the true positive and false positive proportions and used these to derive the standard signal detection measure of d' and criterion (Note that we are refraining from using the term “sensitivity” because it is used to refer to d' in the behavioral science community and to the true positive rate in the medical community.) For the primary analyses, pairs were removed from analysis if either member of the pair produced a d' of less than 0.5. The task was relatively difficult and we had little control over the motivation of participants in online study of this sort. The probability of achieving a $d' > 0.5$ by guessing through an 80 trial block is $\sim 0.6\%$. A cutoff of 0.4 would permit over 2% of blocks to be pure guessing. A $d' > 0.5$ cutoff left 2,080 pairs of blocks. The distribution of those pairs is shown in

Table 5:

		Block N				
		Low, No Feedback	Low, Feedback	High, No Feedback	High, Feedback	
Block N+1	Low, No	29	140	151	134	454
	Low, Feed	92	110	150	218	570
	High, No	261	117	51	117	546
	High, Feed	147	218	118	27	510
		529	585	470	496	2080

Table 5: Counts of the 16 different pairs of Block N and Block N+1.

As can be seen, there is a good, if uneven distribution of pairs. There are fewer pairs on the diagonal where the condition is the same in Blocks N and N+1. In order to run the same block, twice in a row, participants needed to encounter that condition last on Day K and first on Day K+1 since the same condition could not be run twice on the same day. The marginals show that this distribution of the four different conditions is very roughly uniform.

First, we compare performance in the four conditions, regardless of their position the sequence of sessions for each observer. Figure 2 shows the signal detection measures of d' and criterion, “c”. These values cannot be computed if $p(\text{True Positive}) = 1.0$ or $p(\text{False Positive}) = 0.0$. Accordingly, in keeping with one standard practice, we add $\frac{1}{2}$ of a False Positive error to each False Positive count (Hautus, Macmillan, & Creelman, 2021).

[figure not shown]

Figure 2: D' and Criterion as a function of condition. Each dot represents one of 2080 blocks of data. Black lines show mean and +/- 95% CI of the mean.

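### The first-pair check supports the existence of a block-to-block criterion shift, but it cannot rule out a much smaller (for example halved) shift in the typical participant, so it does not show that unequal contribution is unimportant

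*Combined protocol and SAP*

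**What the plan says.** The Observers section of the specific protocol acknowledges that the dataset is unbalanced, with between 2 and 24 blocks per person in the paired analyses. It reports a rerun on each observer's first pair, notes the loss of power, and states that "the main patterns of results, reported below, are found when the dataset is restricted to only blocks 1 and 2". From this it concludes: "we think that the unequal numbers of trials and blocks from different participants is not a significant issue for the present study".

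The section on how one block influences the next describes the same restriction more cautiously: it "preserves the direction of effects but some effects become statistically unreliable because of the loss of power". It does not say which effects became unreliable. Neither section gives the number of first pairs, a mean shift, an SD, a confidence interval or a comparison with the full-data estimate.

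The main criterion tests are one-sample t-tests in each of 16 cells, on all pairs that passed the d' filter (the "cutoff left 2,080 pairs of blocks"). No weighting or clustering by person is described. A separate first-block-only result (p < 0.0001) is given under Statistical Analysis / Results, but it concerns the simple low prevalence effect, not the effect of one block on the next.

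**The concern.** The conclusion that imbalance does not matter is a claim about absence of influence. It needs an estimate from an analysis in which heavy contributors do not dominate, set beside the full-data estimate with its uncertainty. What is reported is agreement in pattern and direction within a much smaller subset.

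An unweighted average over pairs gives most weight to people who chose to run many contests. If the shift differs between committed and casual participants, or changes with experience, the reported effect sizes (Cohen's d of 0.2 to 0.5 after feedback blocks) would not describe the typical participant. This shift is what the document calls its main finding. Because one person can supply up to 23 pairs, treating pairs as independent may also understate the uncertainty of the full-data tests.

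**Working it through.** **Reproducing the stated tests.** For a one-sample t-test, t = d × √n.
- High Feedback repeat pair: n = 27 and p = 0.017 imply d = 0.49, inside the stated 0.2 to 0.5.
- Low No Feedback to High Feedback: n = 147 and d = 0.18 give t = 2.18 and p = 0.031. The stated bound of 0.028 implies d = 0.183, which agrees within rounding.

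The published tests therefore use the number of pairs as the sample size.

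**Imbalance.** In Table 4, the rows for 2 or more blocks sum to 557 people and 2,537 consecutive pairs. The 84 people with 10 or more blocks are 84/557 = 15% of these people and supply 1,251/2,537 = 49% of the pairs. The median person ran 3 blocks, or 2 pairs. Table 4 as a whole sums to 872 people and 3,409 blocks, against 630 people and 2,988 blocks in the text, so these shares are approximate.

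**Number of first pairs (assumed, not stated).**
- People with at least 2 blocks: 630 − 315 = 315 from the text total, or 557 from Table 4.
- Filter retention: 2,080/(2,988 − 630) = 2,080/2,358 = 88%, or 2,080/2,537 = 82%.
- First pairs surviving the filter: 315 × 0.82 = 258 to 315 × 0.88 = 278, or 557 × 0.82 = 457 to 557 × 0.88 = 491.

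**Pairs per cell, at Table 5 shares.** The six off-diagonal cells with feedback in block 1 hold 140, 117, 218 (low prevalence first) and 134, 218, 117 (high prevalence first) of 2,080. The smallest has 258 × 117/2,080 = 14.5 first pairs and the largest 491 × 218/2,080 = 51.5, so about 15 to 50. The High Feedback repeat cell would have only about 3 to 6.

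**What direction can show.** The probability of the expected sign in one cell is Φ(d√n). The product over the six cells, treated as independent, gives:

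| First pairs | All six signs at 0.3 SD | All six at 0.15 SD |
|---|---|---|
| 258 | 0.54 | 0.17 |
| 278 | 0.57 | 0.18 |
| 457 | 0.76 | 0.28 |
| 491 | 0.79 | 0.29 |

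With no effect it is 0.5⁶ = 0.016. Full agreement in sign is therefore about three times as likely at 0.3 SD as at 0.15 SD. Other full effects between the smallest d implied by the p bounds and 0.5 give ratios of about 1.5 to 3.3.

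**What significance can show.** At 0.3 SD, power per cell (two-sided 0.05) is about 0.19 to 0.56, so roughly 1.4 to 2.5 of six cells would be significant. At 0.15 SD the expected number is 0.6 to 0.9. A report that direction held and some effects lost significance fits either size.

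**Pooled contrast.** Take Low Feedback first minus High Feedback first, stratified by block 2 condition with inverse-variance weights and unit SD. The standard error is 0.137 (491 pairs) to 0.190 (258 pairs), so the 95% half-width is 1.96 × SE = 0.27 to 0.37 SD. With shifts of ±0.3 SD the contrast is 0.6. Power against zero is 0.89 to 0.99, but the probability of excluding a halving (a difference of 0.3) is only 0.35 to 0.59.

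**The case against.** The strongest reply is that one pair per person is a sensible check. It gives everyone equal weight and removes dependence within person. The conclusion being protected is mainly directional, and a halved shift would leave it standing. The document also discloses the loss of power. All of this stands, and it is why the check counts as evidence that an effect exists.

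Several stronger readings are tempting but unsupported.
- A reader might infer that the check would look the same under a halved effect. It would not: six agreeing signs are about three times as likely at 0.3 SD as at 0.15 SD, which is weak evidence against a halving but not none.
- A reader might infer that heavy contributors drive the result. Nothing in the documents shows that the shift differs by number of blocks run.
- A reader might see a contradiction between the two descriptions of the check. They are compatible; the Observers section is simply the more confident.
- A reader might extend the criticism to the simple prevalence effect. That has its own one-block-per-person result.

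The choice of 0.3 SD is also open to challenge: p < 0.0005 implies d of at least 0.33 at n = 117 and 0.31 at n = 134. At 0.5 against 0.25 SD, all six signs agree with probability 0.92 against 0.43 (278 pairs) or 0.99 against 0.65 (491 pairs), so the conclusion does not change.

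None of this restores the assurance about size. First pairs also restrict everyone to their least practised blocks, so the check mixes the weighting question with experience.

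**Conclusion.** The concern holds as a limit on what the check can show. For the block-to-block criterion shift, the reported first-pair analysis makes no effect at all implausible, but it leaves open a substantially smaller effect in the typical participant. Even the pooled first-pair contrast would carry a 95% half-width of about 0.27 to 0.37 SD, as large as the 0.3 SD change that a halving from 0.6 would produce, or nearly so. The statement that imbalance is not a significant issue is therefore stronger than its evidence.

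The figures assume 315 or 557 people with at least two blocks, 82% to 88% retention, first pairs distributed as in Table 5, unit SD, independent cells and two-sided 0.05. They also assume that the report of preserved direction covers all six off-diagonal cells. First-pair counts come from the authors' data, not the documents, and could narrow these ranges.

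**What to change.** Keep all pairs. Rerun the main criterion analysis with errors clustered by person, once weighting pairs equally and once weighting each pair by 1/(number of pairs from that person). Report the pooled Low-Feedback-first minus High-Feedback-first contrast under pair weighting, participant weighting and first pair only, side by side, each with the number of people and pairs and a 95% CI. Add the interaction of the contrast with number of pairs run. State how many people ran at least two blocks, since Table 4 and the text imply different numbers.

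In the Observers section, replace the assurance with the size of difference that these intervals exclude, and describe the first-pair result there as cautiously as in the results.

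The data are already posted, so the cost is one rerun and revised wording. The downside is somewhat wider intervals, chiefly for the participant-weighted estimate.
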